#### The specific hypotheses examined are:

- *The primary hypothesis:* 2 years OPUS YOUNG is superior to 2 years TAU (CAMHS or CAMHS+AMHS) examined in all patients aged 12.00 to 17.99 years at inclusion.
- *Planned sensitivity analysis 1*: 1-year OPUS YOUNG vs. 1-year TAU CAMHS in patients ages 12.00 to 16.99 years at inclusion (hence, the patients in this study sample do not turn 18 years during the trial and are solely treated in CAMHS).
- Planned sensitivity analysis 2: 2-years OPUS YOUNG vs. 2-years TAU CAMHS in patients aged 12.00 to 15.99 years at inclusion (hence, the patients in this study sample do not turn 18 years during the trial and are solely treated in CAMHS for the entire intervention period of 2 years).
- Planned sensitivity analysis 3: 2-years OPUS YOUNG vs. 2-years TAU CAMHS + AMHS in patients aged 17.00 to 17.99 years at inclusion (hence, all patients in the TAU group will have undergone transition from CAMHS to AMHS, while the patients in the OPUS YOUNG group will receive OPUS YOUNG treatment for the entire 2 years of intervention.

Due to expected lower sample size in the three planned sensitivity analysis, we do not aim to show statistical superiority of OPUS YOUNG over TAU in these analyses but will examine possible differences by comparing effect sizes.

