#### Randomization

After baseline assessment the participants will be randomized 1:1 to either the experimental treatment (OPUS YOUNG intervention) or standard treatment (TAU). Randomization of the

participant will be centralised and computerised with concealed randomization sequence carried out by the database system used in the Capital Region of Denmark (REDCap) [61]. The randomization concealment mechanism is performed by a computer algorithm saved in REDCap [61]. Randomization cannot be influenced by persons, and block size will be unknown for investigators and clinicians. To optimize the comparability between treatment groups, randomization will be stratified by the two factors: *age* (12-14 years and 15-17 years) and for the main outcome, *PSP* (score 1-44 and score 45-100).

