#### Sample size calculation

Based on the literature concerning the level of psychosocial dysfunction measured with PSP in early onset psychosis (EOP) [118–121] we expect a Standard Deviation (SD) on PSP around SD=13. Concerning the expectations on relevant group difference in improvement during two years of EIS [6,122] we have evaluated the minimal relevant difference (MIREDIF). MIREDIF should represent a meaningful minimal group difference in response in the sense that it would justify a choice between two interventions in a clinical setting. The total PSP scale score range from 1 to 100. The metanalysis [6] on EIS interventions found, for functional outcome measured with Global Assessment of Functioning (GAF, scaled 1-100) including n=1005 participants in 7 studies, a standardized mean difference (difference in mean outcome between groups/standard deviation in outcome among participants) of 0.21 (in the individual 7 studies included ranging from 0.02 to 0.56). With a SD of 13, this equals an expected difference in PSP scores between groups of around 2.73, ranging from 0.26 to 7.28. Based on these findings and the evaluation of what is clinically meaningful when regarding the PSP 10-point ranges of functioning we have decided that it would be clinically relevant to be able to detect a difference of 5 points in outcome score on the total PSP scale between the two interventions. Using a power of 90% and a two-sided alpha of 5%, and expecting a SD of 13 on PSP, the required sample size necessary to detect or reject a difference of at least 5 points between the OPUS YOUNG and TAU group on PSP at endpoint is 284, why we

plan to enrol a minimum of 142 patients in each group. However, to account for drop-outs and due to our relatively long recruitment procedure time, where patients are referred from the clinic and may wait during the assessment period being offered participation, we will include up to 152 patients in each group if necessary, within the recruitment period. This will ensure that patients who are in the recruitment process will still be offered participation in the study even if the minimum of 284 participants has already been enrolled. This is ethically more proper, as patients in the centre entering the recruitment procedure are informed about the potential possibility to be offered inclusion in the study. The last patients will be assessed and included by September 1st, 2023. After this, no more patients will be included.

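### Three age-restricted analyses are to be examined by comparing effect sizes with no interval for the difference between them, and only analyses 2 and 3 share a treatment duration

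*Protocol*

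**What the plan says.** The protocol section on the specific hypotheses gives a primary comparison in all randomised patients and three planned sensitivity analyses:

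- Analysis 1: "1-year OPUS YOUNG vs. 1-year TAU CAMHS in patients ages 12.00 to 16.99 years at inclusion".
- Analysis 2: "2-years OPUS YOUNG vs. 2-years TAU CAMHS in patients aged 12.00 to 15.99 years at inclusion".
- Analysis 3: two years of treatment in patients aged 17.00 to 17.99 at inclusion, all of whom transfer to adult services if allocated to usual care.

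The section explains each cut by when patients turn 18 and therefore leave CAMHS. It expects smaller samples, disclaims any aim of showing superiority in these analyses, and says it "will examine possible differences by comparing effect sizes". It names no treatment-by-age term and no interval for a difference between subsets. Under Randomization, the age strata are 12-14 and 15-17, which match neither the cut at 16 nor the cut at 17.

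**The concern.** These are called sensitivity analyses, but they do not re-estimate the primary quantity under other assumptions. Each changes the population, and the first also changes the time point. In substance they are subgroup analyses. Because the cuts follow the transfer to adult services, and transition support is one of the special components of OPUS YOUNG, readers will set the three results side by side and ask whether the benefit depends on transfer.

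The stated method does not equip them to do so. Separate effect sizes, even if each had its own interval, give no direct measure of uncertainty for the gap between two of them. Two of the three possible comparisons also mix age with treatment duration. The risk is that a chance gap is reported as a finding about age or transfer.

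**Working it through.** **Inputs.** From Sample size calculation: "Using a power of 90% and a two-sided alpha of 5%, and expecting a SD of 13 on PSP"; a relevant difference of 5 points ("it would be clinically relevant to be able to detect a difference of 5 points in outcome score on the total PSP scale"); and a "plan to enrol a minimum of 142 patients in each group", so N = 284. Allocation is 1:1 (Randomization). The protocol gives no age distribution, so three are assumed below.

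**1. The plan's own figure.** N = 4 × (1.960 + 1.282)² × (13/5)² = 284.1, or 42 × 6.76 = 283.9 with the protocol's rounded constant. The stated 284 reproduces, and 142 per arm gives 90% power.

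**2. What each comparison contrasts.**

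| Comparison | Patients | Duration | What differs |
|---|---|---|---|
| 1 v 2 | 2 nested in 1 | 1 v 2 years | age range and duration |
| 1 v 3 | disjoint | 1 v 2 years | age, transfer and duration |
| 2 v 3 | disjoint | 2 years each | age and transfer together; 16.00-16.99 absent |

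Under the three assumed distributions, analysis 2 makes up 189/237 = 80%, 142/213 = 67% or 99/185 = 54% of analysis 1.

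**3. Precision of the cleanest comparison, 2 v 3.** With equal arms, the effect in a subset of n patients has SE = 13 × √(4/n) = 26/√n. For two disjoint subsets, the SE of the gap is 26 × √(1/n₂ + 1/n₃). The 95% half-width is 1.96 × SE. If the true effects are equal, P(|gap| ≥ 5) = 2 × [1 − Φ(5/SE)].

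Second row worked through: 26 × √(1/142 + 1/71) = 3.78; 1.96 × 3.78 = 7.4; 5/3.78 = 1.32, so P = 0.19.

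| Assumed ages | n₂ | n₃ | SE of gap | Half-width | P(gap of 5 or more by chance) | Power for a true 5-point gap | Gap detectable at 80% power |
|---|---|---|---|---|---|---|---|
| even over 12-17 | 189 | 47 | 4.23 | 8.3 | 24% | 22% | 11.8 |
| 25% aged 16, 25% aged 17 | 142 | 71 | 3.78 | 7.4 | 19% | 26% | 10.6 |
| 30% aged 16, 35% aged 17 | 99 | 99 | 3.69 | 7.2 | 18% | 27% | 10.3 |

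Subset sizes are shown rounded; the results use unrounded sizes. Power is for a two-sided 5% z-test. Dropout would widen these intervals, and the baseline adjustment in the planned mixed model would narrow them. Neither is included.

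**The case against.** The strongest defence is that the protocol never says effect modification will be judged from these analyses. No hypothesis about age or transfer is stated. The only contrast named in the sentence is OPUS YOUNG against usual care, so the phrase may mean that each subset's treatment effect is described instead of tested. The subsets also have a sensible purpose: each gives the usual-care arm one service path, and the overlap and unequal durations follow from when patients turn 18. The small samples are conceded. Finally, an interaction term may stand in a statistical analysis plan that is not at hand.

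Much of this stands. A reader might infer that all three comparisons suffer from both overlap and unequal duration. The protocol does not support that: both apply only to analysis 1 against 2, and analysis 2 against 3 has neither. A reader might also infer that the trial commits itself to a conclusion on transfer. It does not.

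It does not remove the point. Comparing several effect sizes across three analyses defined by service path reads more naturally as a comparison between them, and if only description within subsets is meant, the sentence needs to say so. The disclaimer covers superiority within a subset; it supplies no interval for a gap between subsets. What is at issue is the method the protocol states, not its silence on detail.

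**Conclusion.** The point holds in limited form. The stated method gives no measure of uncertainty for a difference between subsets. Analysis 1 cannot be contrasted with either of the others without mixing in treatment duration. For analysis 2 against 3 the duration is equal, but age and transfer are tied and chance is unaddressed: a gap as large as the whole minimal relevant difference would appear in about 18 to 24% of trials with no true difference, and the 95% half-width is about 7 to 8 points. These figures rest on SD 13, 284 patients, equal arms within subsets and assumed age distributions; the conclusion is the same across the range tried.

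Two stronger readings should be resisted. First, a better model would not separate age from transfer, because age at inclusion decides whether a usual-care patient transfers. Second, the primary conclusion is not at risk, since it comes from all randomised patients. The change should be made, but it concerns how exploratory results are reported.

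**What to change.** - Label the three analyses as exploratory subgroup analyses.
- Extend the planned repeated-measures mixed model, fitted to all randomised patients, with treatment × visit × age band (12.00-15.99, 16.00-16.99, 17.00-17.99). Bands are preferable to a linear age term, which could miss a step at transfer.
- Report the treatment-by-age-band contrast at 24 months, chiefly the oldest band against the youngest, with its 95% confidence interval. Take the 24-month subgroup effects from the same model, so that 16-year-olds are included.
- State that analysis 1 is a separate 12-month estimate, not to be contrasted with the 24-month ones.
- State that age and service transfer cannot be separated.

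The cost is one interaction term and some rewording, with no new data or patients. The drawback is a visibly wide interval: power for a true 5-point interaction is only about 22 to 27%, and the interaction detectable with 80% power is about 10 to 12 points. Showing that imprecision is the purpose of the change.

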# **Ethical considerations**

Both the patients and parents/caretaker may be in a state of psychological crisis at the time they are invited to participate in the trial, making it difficult for them to decide whether to participate in the study. There is a risk that they will consider OPUS YOUNG better than TAU, which may affect them when the outcome of randomization is revealed. Still, we do not expect anyone to be affected negatively from being involved in the trial. While OPUS YOUNG is geographically located in a civilian environment, there is still a risk that some participants will find being in OPUS YOUNG treatment associated with stigmatization.

In general, the results of this trial can be of great importance for future health-care planning to benefit young people with a first-episode psychosis. OPUS YOUNG treatment is tailored to meet the patient's individual needs and to support the patient's empowerment and recovery process.

# Written informed consent

All participants are below 18 years of age when invited to participate in the trial, why signed informed consent will be obtained from parents/legal caretakers prior to entering the trial. The adolescents between 15 and 17 years of age will sign written informed consent in addition to the parental consent. Municipal collaborators and clinicians who wish to participate in the interviews regarding user perspectives on trans-sectorial activities will also sign written consent before the interview.

#### Procedures regarding verbal and written information:

Patients, who are deemed eligible to participate in the trial according to the in- and exclusion criteria, as well as their parents/legal caretaker, will be given verbal information about the trial by a health care professional involved in the trial. The verbal information will be provided during regular clinic visits at the CAMHS in the presence of parents/legal caretakers, and in the privacy of an examination room, together with the patient's primary health care provider. The verbal information will be provided in an age-appropriate manner and parents/legal caretakers will be explained their right to have an assessor (e.g., friend or family member) present and in case the parent/legal caretaker should want that, a new appointment will be made for the information meeting. Written information brochures explaining the study background, procedures, aims, and (patient) rights will be provided both to the participant (age-adjusted language for the 12-14 years old and the 15-17 years old, respectively) and the parents/legal caretakers. Both the verbal and written information will inform about participants' rights to withdraw from the trial at any point without it affecting future treatment.

Potential participants and their parents/legal caretakers will have a minimum of 24 hours to consider participation before being contacted by the health professional involved in the trial. The child and their parents/legal caretaker will be informed that the decision must be a shared decision, and both the child as well as their parents/legal caretakers should agree on the child's participation prior to the parents/legal caretakers' consent to the participation. If potential participants and their parents/legal caretakers approve to participate, parents/legal caretakers and the participating youth if 15 years of age or above will sign informed consent prior to initiating any research activities.

Parental Power of Attorney:

A parent/legal caretaker will have the possibility of signing a power of attorney to the other parent/legal caretaker. Parents/legal caretakers will be informed that use of this form is voluntary and can be withdrawn at any time.

#### If only one parent has custody:

If one parent has sole custody, only this parent will give written informed consent to their child's participation in the research project. In this case, the research team will obtain necessary documentation for the parent's sole custody.

#### When the participant turns 18 years of age:

Participants who turn 18 years of age during the trial (within 2.5 years after inclusion) will receive new written and verbal information and be asked to give personal written informed consent in order to continue their study participation.

#### Parental participation:

Each parent/legal caretaker will receive their own written and verbal participant information and informed consent form regarding parental participation. If the parents do not give informed consent to be involved in the trial themselves, the adolescent patient with psychosis can still be included in the trial, if the above criteria for patient participation is fulfilled.

#### Participation of relevant clinicians and municipal collaborators:

At approx. 24 months (follow-up assessment) clinicians participating in the treatment in both the OPUS YOUNG intervention and in TAU will be invited to a semi-structured interview. Only a limited number will be invited from both treatments. Relevant municipal collaborators, taking part in the treatment and collaboration around the group of participants in the trial, will likewise be invited to participate in interviews.

Clinicians and municipal collaborators invited to participate in interviews, will receive written information brochures explaining the study background, procedures and aims, alongside the invitation. Consent will be obtained prior to participation in the interviews. The written information will inform about participants' rights to withdraw consent at any point.

## Feasibility of the study

Based on data from the Danish Psychiatric Central Register and from the CAMHC local register, we expect to be able to recruit a minimum of 284 patients for the trial in the two-year period from June 1, 2021, to September 2023. This is realistic as we expect approximately 200 patients per year to be eligible for participating in the trial in the Capital Region in Denmark. The intervention part of the trial lasts for two years, but due to follow-up assessment six months after end of treatment, participation in the study is 2,5 years, i.e., the last randomized participant will conclude the intervention and trial end-point assessment September 31, 2025, and the 6-month follow-up assessment February 1, 2026 (see study plan, Table 2). The present study is a collaboration between the CAMHC and the adult mental health services (AMHS). Research in child and adolescent mental health is a prioritized focus area in the Mental Health Services of the Capital Region of Denmark, which supports and hosts the present study. Furthermore, the Danish Regions, covering all public health services in Denmark prioritizes in their 2020 recommendations for health research studies focusing on transition from child and adolescent health services to adult health services [128]. The CAMHC has ample experience in conducting clinical studies and trials on early onset psychosis [109,110] and the AMHS harbour the OPUS study [125,129,130], which has conducted trials and carried out a national implementation strategy of EIS in first-episode psychosis for 20 years. We expect patients and relatives to adhere to the two-years duration of OPUS YOUNG treatment as we have 20 years of positive experiences from the adult OPUS treatment, where the case manager's welcoming, assertive, competent, and cooperative approach have proven effectful for adherence. We expect this to be true for a younger age group as well, as the cooperation in CBCM is based on the same principles. Furthermore, as part of our preparations for the trial we have conducted a focus group interview with parents and patients who has been part of the piloting phase of the trial and who has received OPUS YOUNG treatment for periods of 1-6 months at the time of the interview. Both parents and patients expressed very positive evaluations of the OPUS YOUNG treatment, and provided helpful suggestions for adjustments of the program. We acknowledge the efforts needed to recruit and maintain contact with everyone participating in the study. In CAMHS we have conducted several studies recruiting and including a total of more

patients in the OPUS YOUNG study, based on experience from managing the Tolerability and Efficacy of Antipsychotics (TEA) [109,131] trial, as well as our abilities to include patients with early-onset psychosis in clinical prospective neurobiological and cognitive studies [132–138].

than 200 youths with first-onset psychosis below age 18 years. We are confident that we can engage

Furthermore, we have vast experience from the OPUS I trial in which we succeed in an attrition of only 30% of all randomized patients at both 2, 5- and 10-years follow-up [125,129,139] as well as inclusion of 76,5% (90% in Aarhus and 63% in Copenhagen) of eligible patients [139].

## Strengths and limitations

One of the main strengths of this trial is the use of a gold standard RCT design aiming to provide available evidence while minimizing bias. The use of a computer generated random sequence generation handled by an algorithm saved in REDCap [61] reduces the risk of selection bias. The use of blinded outcome assessors for outcomes and the use of intention-to-treat analysis aim to prevent biased effect estimates. All CAMHC patients in the catchment area who potentially meet inclusion criteria are offered to take part in the trial. Due to the very few exclusion criteria, the study will have high external validity.

The study builds on an evidence-based coordinated specialized assertive care model that has been proven efficient in young adults [125,129,140]. The study will provide novel results, since no previous studies have focused on EIS in patients below age 18 years. The current trial is supplemented with innovative and age-appropriate components aiming to target modifiable complications of early psychosis.

The fact that we are not able to blind the participants and staff might increase the risk of performance bias. The OPUS YOUNG treatment is a complex intervention, which makes it difficult to elucidate exactly which components are primarily responsible for the treatment effects. Due to the relatively few cases of psychosis in childhood and early adolescence, our sample will be small relative to adult samples. We have considered a multicentre trial but have weighted the strength of limiting the trial to one geography (short distance for group supervision and rating sessions, close cooperation with one clinic that provides a stable and uniform standard treatment).

# Perspectives

A positive effect of specialized OPUS YOUNG treatment would be of great importance for future health-care planning to benefit young people with a first-episode psychosis. At the time being, we lack evidence to guide clinical practice for best treatment of this very severe mental disorder at a very important time of life. The present alternative is to extrapolate from EIS studies in adults, which cannot be considered evidenced based care, due to the specific needs of children and adolescents with psychosis. Youth have a right to access evidence-based treatment, which in this

case can only be addressed by conducting an RCT of EIS versus TAU. If this model proves to be more effective than TAU, it has an enormous potential for improving symptoms, function, recovery and adherence to treatment, adherence to school/education and thus to community and independent living, while at the same time reducing the need for hospitalization and society costs for this vulnerable patient group. Furthermore, we plan to assess follow-up at five years after end of trial.

## **Project organization and management**

The trial will be carried out in the Capital Region of Denmark and will be co-ordinated by CAMHC and in collaboration with the adult mental health services (AMHS). Here, a series of interventional trials in different phases of schizophrenia spectrum disorders are already being conducted, ranging from high-risk and the early prodromal phase, and the early psychotic phase to later phases with specialized interventions for co-morbid substance abuse and neurocognitive deficits. The steering committee consists of researchers with massive expertise on early and first-onset psychosis and with profound trial experience. Importantly, experienced clinicians are represented in the steering committee to ensure a close collaboration between research and clinic throughout the process. The study group has extensive international networks on EIS and the treatment of psychosis in childhood and adolescence, and the advisory board for the present study will include experts on these areas and on transition and complex interventions.

*Principal investigator*: [name], professor, MD, PhD, senior consultant (child and adolescent psychiatry) and senior researcher, CAMHC.

